**Secondary Aim #1: Characterize the effect of oxygen administration on fetal heart tracing patterns**

*Hypothesis: Oxygen administration will be associated with a rate of persistent Category II FHT that is not different from those exposed to room air.*

Oxygen is typically administered in response to FHT interpretation. Hence, evaluating the effect of oxygen on subsequent FHT is pivotal to labor management. The primary outcome will be resolution of Category II FHT. We will also investigate the effect of oxygen administration on mode of delivery, particularly cesarean delivery for non-reassuring fetal status.

**Secondary Aim #2: Evaluate the safety of oxygen administration by measuring reactive oxygen species (ROS) in maternal and neonatal blood.**

*Hypothesis: Oxygen administration will be associated with increased oxidative stress in maternal and neonatal cord blood as represented by malondialdehyde (MDA).*

Over-oxygenation can result in free radical or ROS formation that have detrimental downstream effects. The presence of reactive oxygen species results in degradation of lipids in the cell membrane and resultant formation of malondialdehyde (MDA), which has been studied as a surrogate for oxidative stress.

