## **Specific Aim 3: Evaluate the safety of oxygen administration by measuring reactive oxygen species in maternal and cord blood**

In order to safely apply maternal oxygen administration for intrauterine fetal resuscitation, the risks of oxygen exposure must be further explored. Over-oxygenation can result in free radical formation, downstream effects of which include cell membrane and DNA damage and resultant carcinogenesis. Although oxygen supplementation is often critical to resuscitation in most settings, studies evaluating hyperoxygenation in adults and animals have shown detrimental cardiac, pulmonary, and cerebral effects. Over-oxygenation in neonates has been shown to be associated with bronchopulmonary dysplasia and retinopathy. Furthermore, reintroduction of oxygen after a period of hypooxygenation can result in adverse effects as the fetus and newborn lack robust antioxidant systems.

One of the primary markers of oxidative stress studied in the literature is malondialdehyde (MDA). The presence of reactive oxygen species results in degradation of lipids and resultant formation of MDA which then modifies endogenous proteins. MDA levels, therefore, have been studied as a surrogate for oxidative stress. (Figure 2)

[figure not shown]

Figure 2: Pathway of oxidative stress

Increased MDA levels in the neonate may be consequential and have been associated with morbidity including hyperbilirubinemia and hypoxic-ischemic encephalopathy. There is also evidence that MDA can be transplacentally transported and thus, both mother and fetus are at risk for downstream effects.

Prior studies have evaluated the relationship between maternal oxygen administration in labor and markers of free radical formation with mixed results. We hypothesize that maternal hyperoxygenation for Category II FHT is associated with increased oxidative stress in the mother and fetus. We will measure MDA in maternal and neonatal cord blood samples as a gage for oxidative stress and to assess the relationship between oxygen administration and subsequent free radical formation.

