## Strategy

The aim of this study is to compare maternal oxygen administration to room air for intrauterine resuscitation of Category II FHT in relation to cord gas parameters, FHT patterns, and oxidative stress in the fetus and mother. The study will be a prospective, randomized non inferiority trial to be conducted at Barnes Jewish Hospital. Current practice at our institution for intrauterine fetal resuscitation of Category II FHT include any of the combination of (1) oxygen administration via nonrebreather face mask at 10L/min (FiO2 approximately 0.80) continued for the duration of labor (2) intravenous fluid bolus (3) maternal repositioning (4) discontinuation of oxytocin. We hypothesize that room air for Category II FHT will be no different than oxygen administration in reducing the degree of fetal metabolic acidosis. This study will include term, singleton patients admitted to Labor & Delivery for spontaneous labor or labor induction. Multiples, fetal anomalies, Category III FHT, umbilical artery doppler abnormalities and preterm pregnancies will be excluded. Additionally, women will be excluded if oxygen is required for maternal indications such as hypooxygenation or cardiopulmonary disease. Our primary objective will be umbilical cord lactate. Secondary objectives include additional cord gas parameters including umbilical artery pH, umbilical artery base deficit, and umbilical vein oxygen saturation; FHT categorization and deceleration patterns; maternal and umbilical cord blood measurement of malondialdehyde.

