#### Specific Aim 2: Characterize the effect of oxygen administration on fetal heart tracing patterns

The patient's primary nurse will document the time at which intervention is initiated. A blinded investigator will then retrospectively assess FHT categorization and deceleration patterns both pre and post intervention.

Specific Aim 3: Evaluate the safety of oxygen administration by measuring ROS in maternal and neonatal blood

We will be measuring serum MDA in both cord and maternal blood as a marker of oxidative stress. MDA is a byproduct of lipid peroxidation, which occurs as a result of oxidative stress. Measurement of Thiobarbituric Acid Reactive Substances (TBARS) is a commonly used assay

for quantifying MDA This assay is performed by fluorometrically measuring the MDA-TBA complex formed in plasma or serum by the reaction of MDA and TBA.

Upon delivery of the infant, an additional sample of umbilical artery blood will be collected for this analysis. An optional sample of maternal blood will also be drawn within 60 minutes of delivery. Both blood samples will be centrifuged to collect plasma which will then be stored at -80°C until the TBARS assay is performed.

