## **Statistical Analysis**

Intention-to-treat (primary analysis) and per protocol analyses will be performed. Chi-squared and Fisher's exact tests will be used to compare categorical variables as appropriate. Continuous variables will initially be assessed for distribution pattern via the Kolmogorov-Smirnov test. Normally distributed variables will be compared using Student's t-tests and non-normally distributed variables will be analyzed with the Mann-Whitney U test. These analyses will be supplemented by multivariable logistic regressions to adjust for confounders.

Tests with  $p < 0.05$  will be considered statistically significant. Analyses will be performed using Stata (Stata Corp., College Station, TX).

For the primary outcome of lactate, 95% confidence intervals (CI) will be calculated for the mean cord lactate levels in each group. Comparison of the 95% CI in each group will then determine non-inferiority or inferiority.

Additional interaction analyses for the primary outcome will be performed for the following subgroups:

- 1) Presence of chronic medical conditions (hypertensive disorder, diabetes)

- a. Patients with hypertensive disorders (chronic hypertension, gestational hypertension, preeclampsia)
- b. Patients with diabetes mellitus (gestational diabetes, T1DM, T2DM)
- 2) Recurrent late decelerations pre intervention
- 3) Recurrent variable decelerations pre intervention
- 4) Prolonged deceleration pre intervention
- 5) Fetal tachycardia pre intervention
- 6) Fetuses with intrauterine growth restriction
- 7) Chorioamnionitis
- 8) Within oxygen group: Duration of oxygen exposure
  - a. <50% of total duration of active labor (onset of active labor to delivery)
  - b. >50% of total duration of active labor (onset of active labor to delivery)

Odds ratios and 95% CI will be calculated for the secondary outcome of persistent Category II FHT. Kaplan-Meir analyses will be performed for fetal monitoring analyses.

For the outcome of maternal and cord blood MDA, a fetal MDA will be calculated by subtracting umbilical artery MDA from maternal MDA for each sample. The calculated mean fetal MDA and maternal MDA values will then be compared between groups using either Student t test or Mann Whitney U test.

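### The derived fetal MDA is maternal minus umbilical artery MDA: it falls as cord MDA rises, cancels any oxygen effect shared by mother and fetus, and displaces a direct comparison of cord MDA

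*Combined protocol and SAP*

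**What the plan says.** The hypothesis under Secondary Aim #2 (Specific Aims) is: "Oxygen administration will be associated with increased oxidative stress in maternal and neonatal cord blood as represented by malondialdehyde (MDA"). It predicts a rise in both compartments, in the same direction. The Strategy section lists among the secondary objectives "maternal and umbilical cord blood measurement of malondialdehyde", and its Specific Aim 3 paragraph adds: "We will be measuring serum MDA in both cord and maternal blood as a marker of oxidative stress". All three concern MDA as measured in each compartment.

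The Statistical Analysis section then replaces the measured cord value with a derived one: "a fetal MDA will be calculated by subtracting umbilical artery MDA from maternal MDA for each sample". It continues: "The calculated mean fetal MDA and maternal MDA values will then be compared between groups", by t-test or Mann-Whitney test. UA MDA as measured is not among the quantities named.

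On sampling, the Specific Aim 3 paragraph of the Strategy section plans an additional UA sample at delivery without calling it optional. Of the mother it says: "An optional sample of maternal blood will also be drawn within 60 minutes of delivery".

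No reason is given for the subtraction. The nearest is a remark in Background/Significance, Specific Aim 3: "There is also evidence that MDA can be transplacentally transported".

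**The concern.** Four things go wrong together.

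- **Direction.** The score is maternal minus UA, so each unit of extra MDA in the fetal artery lowers it by one unit. Oxidative harm confined to the fetus would be reported as less fetal MDA on oxygen.
- **Cancellation.** The hypothesis is that oxygen raises both values. Subtracting one from the other removes the common part of the effect the aim sets out to detect.
- **Omission.** The quantity the hypothesis names for the neonate, cord MDA, has no named comparison between arms.
- **Avoidable loss.** The score needs both samples. A neonate with a usable cord sample drops out whenever the optional maternal sample is missing.

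This is the only analysis of neonatal oxidative stress that the plan spells out. It supports the suggestion, in Specific Aims and in the section on potential impact, that room air may be the safer option. As written, it could show the reverse of what happened in the cord blood, or show nothing when cord MDA had risen.

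**Working it through.** **Algebra (no numerical assumption needed).** Let M and U be maternal and UA MDA, and let dM and dU be the oxygen-minus-room-air differences in their means. The plan's fetal value is D = M − U, so its between-arm effect is

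effect on D = dM − dU.

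| True effect of oxygen | Effect on D | How D would read |
|---|---|---|
| Fetus only (dM = 0, dU > 0) | −dU | fetal MDA lower on oxygen |
| Mother only (dM > 0, dU = 0) | +dM | fetal MDA higher on oxygen, though cord MDA is unchanged |
| Equal rise in both (dM = dU) | 0 | no effect |
| Both rise, unequally | sign of dM − dU | either direction |

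The hypothesis (dM > 0 and dU > 0) therefore predicts no sign for D. Writing the score as U − M would correct the direction but not the cancellation. Only a comparison of U between arms estimates dU.

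**Sample size used for illustration.** The plan has no sample size for MDA, so I use the lactate figures. The margin is 0.30 × 3.5 = 1.05 mmol/L, with SD 1.6, one-sided alpha 0.025 and 90% power:

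n per arm = 2 × (1.960 + 1.282)² × 1.6² / 1.05² = 48.8, rounded up to 49, or 98 in total.

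This reproduces the plan's 98. The planned 114 is 57 per arm, which matches 49 × 1.15 = 56.4 rounded up.

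**Power.** The documents give no MDA effect, SD or maternal-cord correlation. Assumptions: equal SDs (set to 1), dU = 0.6 SD, maternal-cord correlation rho from 0.2 to 0.8, two-sided alpha 0.05, and complete pairs. Then SD(D) = √(2 − 2·rho), and the noncentrality parameter is

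- direct comparison of U: 0.6 / √(2/n);
- difference score: (dM − 0.6) / [√(2 − 2·rho) × √(2/n)].

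At n = 49, √(2/49) = 0.202. The direct comparison has noncentrality 0.6/0.202 = 2.97. For the difference score with dM = 0.3 and rho = 0.5, SD(D) = 1 and the noncentrality is −0.3/0.202 = −1.48. Noncentral-t results:

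| Analysis | 49 per arm | 57 per arm |
|---|---|---|
| U compared directly | 84% | 89% |
| D, dM = 0.6 (equal rise), any rho | 5% | 5% |
| D, dM = 0.3, rho = 0.2 | 21% | 24% |
| D, dM = 0.3, rho = 0.5 | 31% | 35% |
| D, dM = 0.3, rho = 0.8 | 64% | 71% |

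In the three rows with dM = 0.3, the expected effect on D is −0.3 SD. Nearly every significant result would therefore say that fetal MDA is lower on oxygen, although cord MDA has risen by 0.6 SD. The 5% row is the false-positive rate of the test.

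**Missing maternal samples.** The documents give no uptake rate, so I attach no figure. Any shortfall reduces n for D but not for U.

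**The case against.** The case on the other side has five parts.

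1. *A general rule could cover cord MDA.* The Statistical Analysis section opens with a rule for continuous variables ("non-normally distributed variables will be analyzed with the Mann-Whitney U test", with t-tests for normal ones). Other cord-gas outcomes have no analysis of their own, so that rule must serve them and could serve cord MDA. But the MDA paragraph announces that it deals with the maternal and cord MDA outcome and then names what is compared. Specific text governs over general. At best, a direct cord comparison is left to inference.
2. *The sign may be a drafting slip, and a two-sided p-value is the same for M − U and U − M.* Both are possible or true. Nothing in the documents says it is a slip, and the direction of the estimate is what a reader will interpret. Correcting the order leaves the cancellation in place.
3. *Removing the maternal contribution may be the purpose.* Placental transfer makes this conceivable, but no passage states such an aim. If it were the aim, the order should be UA minus maternal. The stated hypothesis concerns MDA in cord blood, whatever its origin.
4. *Maternal MDA is compared separately, so a shared effect would still show in the mother.* This stands. What is lost is the fetal half of the hypothesis.
5. *The power figures are hypothetical, and patient choice need not cause bias.* Both stand. The 5% needs exactly equal rises, and a larger maternal than fetal rise would make D positive. If mothers choose at consent, before randomization, the missing samples cost precision without biasing the comparison. The documents do not say when they choose.

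**Conclusion.** The concern holds. As written, the derived fetal MDA moves opposite to cord MDA, loses any effect common to mother and fetus, and takes the place of the comparison that the hypothesis calls for. These conclusions follow from the definition and rest on no assumed number.

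The size is illustrative only. Under the stated assumptions (49 per arm, equal SDs, a 0.6 SD rise in UA MDA), power falls from 84% for a direct comparison to 5% when the maternal rise is equal. With a maternal rise half as large it is 21% to 64%, with the sign reversed.

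MDA is a secondary outcome, and the lactate analysis and its sample size are untouched. The definition still must be corrected, because the variable does not measure what its name and the aim require. If it is left open, the choice among M − U, U − M and U could be made after the results are known.

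**What to change.** Revise the MDA paragraph of the Statistical Analysis section before any comparison by arm:

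- Make UA MDA itself the fetal endpoint, compared directly between arms using every available cord sample, whether or not a maternal sample exists.
- Compare maternal MDA separately, among women with a maternal sample, and report the number sampled in each arm.
- If a difference is still wanted, define it as UA minus maternal, call it a feto-maternal gradient, state its direction, limit it to complete pairs and label it exploratory. Drop the name fetal MDA for it.

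The cost is SAP wording only. The UA and maternal samples and the assay are already planned, so no extra blood, laboratory work or patients are needed.

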### **Sample size analysis**

A review of previously collected data from our institution of 5182 term singleton pregnancies revealed a mean cord lactate of  $3.5 \pm 1.6$  mmol/L in women with Category II FHT within 30 minutes of delivery. All of these deliveries were managed using our current protocol of routine oxygen administration for Category II FHT. Given the normal mean lactate seen in our population of patients with Category II FHT, a noninferiority approach was selected to test our hypothesis that room air is not inferior to oxygen administration in treating Category II FHT. A total sample size of 98 patients will be needed to detect a non-inferiority margin of 30% with 90% power, using a one-sided two-sample t-test (alpha 0.025). To accommodate a 15% drop out/cross over rate, a total of 114 patients will be needed. We plan on performing an initial compliance run-in of 6 patients making the total enrollment 120 patients. Data analysis will only be performed on the 114 patients enrolled after the initial 6 patients enrolled/randomized in the compliance run-in/pilot. Previous studies have shown an increased risk for neonatal morbidity with cord lactate cut-offs ranging from 3.2-6.0. The margin of noninferiority was

therefore set at a lactate cut-off of 4.5, above which there is a clear association with neonatal morbidity.

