Consent will be obtained at time of admission to Labor & Delivery. Randomization to either the oxygen group or room air group will be performed when the patient is in active labor (defined as regular contractions and  $\geq 6$  cm cervical dilation) and develops Category II FHT necessitating intrauterine resuscitation as determined by the care provider team (Figure 3). This will be performed via a computer-generated randomization sequence in a 1:1 ratio. Patients randomized to the oxygen group will receive the above stated current management of oxygen via nonrebreather face mask at 10L/min and “per-protocol” defined as receiving the mask for at least 90% of the remaining duration of labor including during cesarean delivery. Patients randomized to the room air group will not receive oxygen for Category II FHT unless otherwise required for maternal indications. Alternative and/or additional intrauterine resuscitation techniques for both groups (i.e. fluid bolus, maternal repositioning, and discontinuation of oxytocin) will be left to

the discretion of the medical team. The initial 6 patients consented and randomized will be part of a compliance run-in with the same protocol as above.

[figure not shown]

Figure 3: Flow diagram for randomization and treatment groups  
 L&D: Labor and Delivery FHT: fetal heart tracing

Specific Aim 1: Determine the effect of maternal oxygen administration for Category II FHT on neonatal cord gas parameters

After delivery of the infant, a segment of the umbilical cord will be removed with immediate collection of umbilical artery and vein samples by trained providers. These samples will be sent to the hospital laboratory for routine cord gas measurements as is universally practiced on our Labor and Delivery unit.

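### The non-inferiority margin is stated both as 30% and as a lactate cut-off of 4.5; the two agree only at an oxygen-arm mean of 3.46 mmol/L, and the analysis section names neither.

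*Combined protocol and SAP*

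**What the plan says.** All references are to the combined protocol and SAP.

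- **Sample size analysis, planning values.** The mean lactate of 3.5 mmol/L (SD 1.6) comes from the institution's own term singleton deliveries, "in women with Category II FHT within 30 minutes of delivery". The next sentence adds: "All of these deliveries were managed using our current protocol of routine oxygen administration for Category II FHT".
- **Sample size analysis, margin as a percentage.** "A total sample size of 98 patients will be needed to detect a non-inferiority margin of 30% with 90% power". The calculation is for a t-test at a one-sided alpha of 0.025.
- **Sample size analysis, margin as a cut-off.** At the end of the section the margin is said to be "therefore set at a lactate cut-off of 4.5, above which there is a clear association with neonatal morbidity".
- **Strategy, entry criterion.** Randomization, in a 1:1 ratio, takes place when a woman in active labor at 6 cm or more "develops Category II FHT necessitating intrauterine resuscitation as determined by the care provider team". No limit is set on the time to delivery.
- **Statistical Analysis, decision rule.** A 95% confidence interval is calculated for the mean in each arm, and comparing the two intervals decides non-inferiority. No margin appears there.

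No section says which form governs, whether the 30% applies to 3.5 or to the observed oxygen-arm mean, or whether 4.5 limits the room-air mean or only explains the size of the margin.

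**The concern.** The margin is the quantity on which a non-inferiority verdict turns. Here it has two forms that match, approximately, at one planning value. A percentage margin widens as the control mean rises; a fixed ceiling leaves less room. If the oxygen-arm mean is above 3.46, the 30% form is the more lenient; below it, the 4.5 form is. The choice between them could then be made after the data are seen.

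There is a reason in the documents why the oxygen-arm mean might not be 3.5. The planning figure describes tracings in the last half hour before birth. The trial randomizes at a Category II tracing that the team judges to need resuscitation, at any time from 6 cm onward. This is one possible cause of a shift; chance or a change in case mix would have the same effect.

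**Working it through.** **Inputs.** Mean 3.5, SD 1.6, margin 30%, cut-off 4.5, one-sided alpha 0.025, power 90%, total 98 (Sample size analysis); 1:1 allocation (Strategy). The true difference is taken as zero, as the stated size implies.

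**1. Reproduce the plan's figure.** Per-arm size, normal approximation: n = 2 × (1.960 + 1.282)² × SD² / margin².
- 30% form: margin = 0.30 × 3.5 = 1.05 (limit 3.5 + 1.05 = 4.55). n = 2 × 10.51 × 2.56 / 1.1025 = 48.8, so 49 per arm, 98 in total. This matches.
- 4.5 form: margin = 4.5 − 3.5 = 1.00. n = 2 × 10.51 × 2.56 / 1.00 = 53.8, so 54 per arm, 108 in total (110 with the exact t calculation). This does not match.

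So the trial was sized on 1.05. With 49 per arm, exact t power is 89.5% for a margin of 1.05 and 86.5% for 1.00.

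**2. Where the two forms agree.** Let m be the oxygen-arm mean. Then 1.3 × m = 4.5 gives m = 3.46, and only there.

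**3. How far they part.** The documents give no mean for the randomized population, so the values other than 3.5 are assumptions. Power is for 49 per arm, SD 1.6, no true difference, and a margin fixed in advance at the value shown.

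| Oxygen-arm mean | 30% margin (limit) | Power | 4.5 minus mean | Power |
|---|---|---|---|---|
| 3.0 (assumed) | 0.90 (3.90) | 78.7% | 1.50 | 99.6% |
| 3.5 (planned) | 1.05 (4.55) | 89.5% | 1.00 | 86.5% |
| 4.0 (assumed) | 1.20 (5.20) | 95.7% | 0.50 | 33.4% |

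**4. Opposite verdicts on the same data.** The half-width of the 95% interval for the difference is 1.985 × 1.6 × √(2/49) = 0.64. For one arm's mean it is 2.011 × 1.6 / √49 = 0.46.
- Oxygen 4.0, room air 4.2: upper limit 0.20 + 0.64 = 0.84. This is below 1.20 (and below a fixed 1.05), so it passes the 30% form. It is above 0.50, and the room-air arm's own upper limit is 4.2 + 0.46 = 4.66, so it fails the 4.5 form on either reading.
- Oxygen 3.0, room air 3.5: upper limit 0.50 + 0.64 = 1.14. This is above 0.90 (and above 1.05), so it fails the 30% form. It is below 1.50, and the room-air arm's upper limit is 3.96, so it passes the 4.5 form on either reading.

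**5. How often.** I simulated trials with no true difference and 49 per arm. Comparing the upper limit with 30% of the observed oxygen mean, and then with 4.5 minus that mean, gave different verdicts in about 13% of trials at a common mean of 3.5, 24% at 3.0 and 66% at 4.0. If the 30% is instead fixed at 1.05 and the 4.5 is a ceiling on the room-air arm's upper confidence limit, the disagreement is about 10% at 3.5 and 34% at 4.0.

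**The case against.** The strongest reply is that there is only one margin. Thirty percent of 3.5 gives a limit of 4.55, roughly 4.5, so the percentage can be read as the size and the cut-off as its clinical rationale. On that reading the margin is fixed at about 1.0 to 1.05, and the large divergence arises only if 30% floats with the observed mean or 4.5 acts as a separate limit. The reading is reasonable and may be what was meant. But the text does not say so: it states that the margin was set at the cut-off, and the analysis section supplies nothing to settle it. Even on this reading, 1.00 and 1.05 imply different sample sizes.

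A second reply concerns the power figures in step 3. They hold only for margins fixed in advance at each assumed mean. If 4.5 is a ceiling on the room-air arm's upper confidence limit, power is about 99% at a mean of 3.5 and 57% at 4.0. This stands, and it shows that the cut-off form itself has more than one reading.

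A reader might also infer that the planning mean is wrong for this trial, because the source group would include mild tracings that prompted no action. The documents do not support that. They say all the source deliveries were managed under the routine oxygen protocol, which is also the control regimen, so a no-action subgroup is conjecture. Only the timing difference and the team-judgment condition for randomization are on the page, and neither gives a direction or size for any shift.

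**Conclusion.** The concern holds as a conflict between two stated forms of the margin, left open by a decision rule that names no margin. At the planning mean the gap is small: 1.05 against 1.00 mmol/L, 98 patients against 108 to 110, and 89.5% against 86.5% power at 49 per arm. Away from 3.46 it widens, and opposite verdicts on the same data are possible.

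The different timing of the planning cohort is a plausible reason for the oxygen-arm mean to differ from 3.5, but it is not the root of the problem and is not shown to have any particular effect. Means of 3.0 and 4.0 are illustrations. The calculations also assume SD 1.6, 49 evaluable per arm and no true difference. The sample size arithmetic is sound for a margin of 1.05.

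**What to change.** Before any comparison of lactate by arm:

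1. In the sample size section, state one absolute margin for the difference in mean umbilical artery lactate, room air minus oxygen, to apply whatever oxygen-arm mean is observed. Two values follow from the plan's own figures:
   - 1.05 mmol/L (30% of 3.5), which keeps 98 evaluable patients at about 90% power, with 4.5 described as approximate rationale only; or
   - 1.0 mmol/L (4.5 minus 3.5), with power at 98 evaluable restated as about 86.5%.
2. In the statistical analysis section, replace the comparison of the two arm-specific intervals. Conclude non-inferiority if the upper limit of the two-sided 95% confidence interval for the between-arm difference is below that margin. Remove 30% and 4.5 as decision limits.
3. State that 3.5 ± 1.6 describes tracings within 30 minutes of delivery rather than the randomization criterion, and report the observed oxygen-arm mean beside 3.5. A fixed difference does not by itself hold the room-air mean near 4.5: with an oxygen mean of 4.0, a margin of 1.0 reaches 5.0. Readers need the observed mean to judge whether the rationale still applies.

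The cost is a wording amendment and no extra patients. If 1.0 is chosen, the stated power falls from 90% to about 86.5%.

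### The stated sample sizes (98, then 114) do not reproduce under the plan's own t-test and 15% loss; the gap is minor at the 30% margin and larger at the 4.5 cut-off

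*Combined protocol and SAP*

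**What the plan says.** All the sizing is in one paragraph of the combined protocol and SAP, under Sample size analysis. It takes a cord lactate of 3.5 ± 1.6 mmol/L from institutional data and states: "A total sample size of 98 patients will be needed to detect a non-inferiority margin of 30% with 90% power". The test named is a one-sided two-sample t-test at alpha 0.025. The allowance for loss follows: "To accommodate a 15% drop out/cross over rate, a total of 114 patients will be needed". Six run-in patients bring enrolment to 120, but "Data analysis will only be performed on the 114 patients enrolled after the initial 6 patients". The paragraph ends with a second description of the margin, which is "therefore set at a lactate cut-off of 4.5".

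Two other sections matter. The Strategy section specifies a "computer-generated randomization sequence in a 1:1 ratio". The Statistical Analysis section says: "Intention-to-treat (primary analysis) and per protocol analyses will be performed". The plan does not say how 98 was computed, how 114 was obtained from it, or how the 15% divides between drop-outs and cross-overs.

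**The concern.** A reader should be able to rebuild the sample size from the inputs printed beside it. Here three things get in the way. The base of 98 is slightly too small for the test named. The 114 does not leave 98 after the loss it is meant to cover. And the margin is given in two forms that are not the same number. All three move the figures in the same direction, towards a power somewhat below the stated 90%.

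At stake is how the result will be read. In a non-inferiority trial, power for the declared margin tells readers whether a failure to show non-inferiority could simply reflect too few patients. The per-protocol analysis also carries weight in this design, because cross-over makes the arms more alike.

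**Working it through.** **Inputs**
- Mean 3.5 and SD 1.6 mmol/L, one-sided alpha 0.025, power 90%, loss 15%: Sample size analysis. The ± 1.6 is read as an SD.
- Allocation 1:1: Strategy.
- Margin M, first form: "non-inferiority margin of 30" percent of 3.5, so 0.30 × 3.5 = 1.05 mmol/L.
- Margin M, second form: 4.5 − 3.5 = 1.0 mmol/L.
- True difference zero: an assumption. The plan gives no number, but its hypothesis is that room air is no different from oxygen.

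**1. Reproducing 98.** The normal approximation is n per arm = 2 × [SD × (z0.975 + z0.90) / M]². With z values 1.960 and 1.282, this is 2 × [1.6 × 3.242 / 1.05]² = 48.8, rounded up to 49 per arm and 98 in total. The stated figure is reproduced exactly.

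**2. The same size under the named t-test.** Power is the probability that a noncentral t variable, with 2n − 2 degrees of freedom and noncentrality M / (SD × √(2/n)), exceeds the 97.5th percentile of the central t.
- 49 per arm: noncentrality 1.05 / (1.6 × √(2/49)) = 3.25, power 89.5%.
- 50 per arm: noncentrality 1.05 / (1.6 × 0.2) = 3.28, power 90.1%.

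The t-test therefore needs 100, not 98.

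**3. The allowance for loss.**
- 114 × 0.85 = 96.9, about 97, which is below 98. This check needs no guess about the formula used.
- Keeping 98 after a 15% loss: 98 / 0.85 = 115.3, so 116.
- Keeping 100: 100 / 0.85 = 117.6, so 118.
- A possible origin of 114: 49 × 1.15 = 56.35, rounded up to 57 per arm. Applied to the total, 98 × 1.15 = 112.7 gives 113, so 114 arises this way only if rounding is done by arm. This is an inference from a numerical match.

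**4. Size for the second margin.** At M = 1.0 the normal approximation gives 53.8, so 54 per arm and 108 in total. The t-test needs 55 per arm, or 110, and 110 / 0.85 = 129.4, so 130.

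**5. Power by the t-test with 114 enrolled after the run-in**

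| Patients with an outcome in the analysis | M = 1.05 | M = 1.0 |
|---|---|---|
| about 97 (full 15% removed) | 89.2% | 86.1% |
| 114 (none removed) | 93.5% | 91.1% |

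At M = 1.05 power stays at or above 90% while at least 100 patients are analysed, which allows 14 of 114 (12.3%) to be lost. At M = 1.0 it needs 110, which allows 4 of 114 (3.5%).

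**The case against.** The strongest reply is that this is rounding. At the 30% margin, with the full 15% removed, power is 89.2%, only 0.8 points below 90%. An SD of 1.578 in place of 1.6 would restore 90%, and the plan gives its SD to one decimal. The base step and the loss step are each worth about two patients. That stands, and at this margin the point is one of reporting.

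A second reply is that the 15% mixes drop-outs with cross-overs. Intention to treat is primary, and cross-overs stay in that set; only patients without a lactate value drop out of it. The Strategy section also describes cord gas measurement as universal on the unit. This stands too. A reader might infer that the trial fails to deliver 90% power for its primary analysis. The documents do not support that: they do not split the 15%, and at 1.05 the primary analysis keeps 90% unless more than about 12% of patients lack an outcome.

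A third reply is that most of the larger shortfall comes from the margin, not from the sample-size arithmetic. That is correct: of the gap between 90% and 86.1%, 89.2 − 86.1 = 3.1 points are due to moving from 1.05 to 1.0. But power cannot be restated without settling the margin. Nor can the 4.5 reading be set aside as loose wording, since it is the form the section justifies by neonatal morbidity.

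These replies limit the size of the problem. They do not make 114 less 15% equal 98, or make 1.05 equal 1.0.

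**Conclusion.** The point holds as a correction to stated figures. Under the section's inputs, 98 is a normal-approximation size where the named t-test needs 100, and 114 with a 15% loss leaves about 97. Consistent targets are 116 from a base of 98 and 118 from a base of 100, against 114 stated.

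If the margin is 1.05 mmol/L the consequence is minor. If it is 1.0 mmol/L, a full 15% loss leaves power about 4 points short of the stated 90%, although the intention-to-treat analysis would still exceed 90% with every outcome present.

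The calculations assume SD 1.6 in both arms, a true difference of zero, equal arms, and losses unrelated to outcome. The 97-patient figures apply when the whole 15% leaves the analysis, which describes the per-protocol set better than the primary one. The documents show figures that do not reproduce and a margin given in two ways. They do not show an underpowered primary analysis.

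**What to change.** Keep enrolment at 114 plus the 6 run-in patients and rewrite the sizing paragraph:

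1. State one non-inferiority margin as a difference in mean lactate in mmol/L, and reconcile the 30% and the 4.5 cut-off with it. The choice should be made without sight of outcome data by arm.
2. Compute power by the named t-test, with the SD and the assumed true difference written out.
3. State that 114 with a 15% loss leaves about 97, not 98. Any future inflation should divide by 0.85.
4. Give power for both analysis sets. For per protocol, with about 97 evaluable, it is about 89% at 1.05 or about 86% at 1.0. For intention to treat, count only missing lactate values as lost and state the rate expected; the ceiling with all 114 is 93.5% at 1.05 or 91.1% at 1.0.

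The cost is one paragraph and no extra patients. The downside is that the stated power becomes slightly less favourable, mainly for the per-protocol analysis.
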